6.7. Subject Disposition

Because this is a long-term study in an elderly patient population with multiple comorbidities, patient discontinuation is of particular concern. Efforts will be undertaken to reduce patient discontinuations and to obtain information on patients initially categorized as lost to follow-up.

From the randomized population, the percentage of patients withdrawing from each treatment group will be summarized. Patients discontinuing treatment due to the sponsor's decision to end the phase 3 program, following the futility analysis, will have "sponsor decision" as reason for discontinuation. From the Safety – PC population, the percentage of subjects discontinuing from each treatment group will be compared between groups using Fisher's Exact test. Comparisons using Fisher's Exact test will be done for the overall percentage of patients who discontinue and also for each specific reason for discontinuation. From the Safety – DS population, the percentage of subjects discontinuing from each treatment group will be summarized.

6.8. Subject Characteristics

Baseline subject characteristics will be summarized for the Randomized population by treatment group and overall.

Summaries will include descriptive statistics for continuous and categorical measures. Fisher's Exact test will be used for treatment group comparisons of categorical data. For continuous data, analysis of variance (ANOVA), with independent factors for treatment, will be used. Subject characteristics that will be summarized include:

- age (continuous and categorized into 55-64, 65-74, and 75+)
- gender
- race (and ethnicity)

- height
- body weight
- body mass index (weight (kg) / [height (m)]2)
- region
- tobacco use
- alcohol use
- caffeine use
- years of education
- work status
- having 1 or more first degree relatives with AD
- AChEI and/or memantine use at baseline
- time since diagnosis
- amyloid inclusion method (PET, CSF, historical PET)
- Mini Mental State Examination (MMSE) score at Visit 1
- Baseline severity of impairment as measured by ADAS-Cog13, ADAS-Cog11 ADCS-ADL total score and instrumental (ADCS-iADL) and basic subscores (ADCS-bADL), iADRS, CDR Sum of Boxes, RBANS, NPI, RUD-Lite, EQ-5D Proxy, and FAQ.
- APOE4 genotype ($\varepsilon 2/\varepsilon 4$, $\varepsilon 3/\varepsilon 4$, $\varepsilon 4/\varepsilon 4$, no $\varepsilon 4$) and carrier status (carrier [$\varepsilon 2/\varepsilon 4$, $\varepsilon 3/\varepsilon 4$, $\varepsilon 4/\varepsilon 4$], noncarrier [$\varepsilon 3/\varepsilon 3$, $\varepsilon 2/\varepsilon 2$, $\varepsilon 3/\varepsilon 2$])

6.9. Treatment Compliance

Treatment compliance will be assessed in the Safety – PC population. Subjects who consume at least 80% of the prescribed daily dose during this study will be considered compliant. The percentage of compliant subjects will be compared across treatment groups using Fisher's Exact test.

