## 7. Treatments

#### 7.1. Treatments Administered

LY3314814 film-coated tablets in two different strengths (20 and 50 mg) and matching placebo will be manufactured and provided by AstraZeneca.

Investigational product will be dispensed as outlined in the Schedule of Activities (Section 2). Since the LY3314814 20 mg tablets and the LY3314814 50 mg tablets look different, the investigational product will be blinded using double-dummy technique. For study treatments (blinded) during the Placebo-Controlled treatment period see (Visit 2 to Visit 16) Table 7.1.

For study treatments (blinded) during the Delayed-Start Period (Visit 16 to 30), patients who were on placebo will be switched to either LY3314814 20 mg or LY3314814 50 mg; blinding is maintained to prior allocation and dose (see Table 7.1).

Table 7.1. Treatment Regimens for Placebo-Controlled and Delayed-Start Periods

Dogimon	Placebo-Controlled Period Dose	Delayed-Start Period Dose (Visit 16 through Visit 30)
Regimen	(Visit 2 through Visit 16)	(visit to through visit 50)
LY Dose Group 1	20 mg LY	20 mg LY
	Placebo to Match 50mg LY	Placebo to Match 50mg LY
LY Dose Group 2	50 mg LY	50 mg LY
•	Placebo to Match 20mg LY	Placebo to Match 20mg LY
Placebo	Placebo to Match 20mg LY	20 mg LY and Placebo to Match 50mg LY
	Placebo to Match 50mg LY	OR
	C	50 mg LY and Placebo to Match 20mg LY

Abbreviations: LY=LY3314814

The investigator or his/her designee is responsible for the following:

- explaining the correct use of the investigational product to the patient
- verifying that instructions are followed properly
- maintaining accurate records of investigational product dispensing and collection
- at the end of the study returning all unused medication to the Sponsor, or its
  designee, unless the sponsor and sites have agreed all unused medication is to be
  destroyed by the site, as allowed by local law

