## 7.6. Treatment Compliance

Patient compliance with study medication will be assessed at each visit by direct questioning and counting returned tablets. The patient should be instructed to retain all empty drug packages after using up the medication in the package and to bring the empty packages and any unused medication to the clinic at each visit so that the clinic staff can record the amount of medication used since the last visit.

Compliance will be assessed at telephone visits via questioning of the patient and/or study partner.

Patients who consume at least 80% of the prescribed daily dose during this study will be considered compliant. Similarly, a patient will be considered significantly noncompliant if he or she is judged by the investigator to have intentionally or repeatedly taken more than the prescribed amount of medication. Patients regarded as non-compliant may be discontinued at the investigator's discretion, in consultation with the medical monitor.

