## 8.1.2. Temporary Discontinuation from Study Treatment

Treatment can be temporarily discontinued (examples include short-term treatment using a prohibited drug, uncertain adverse event, hospitalization). Re-starting investigational product is based on the Principal Investigator's judgment. The maximum permissible treatment suspension is a total of 6 weeks over the duration of the study. Temporary treatment discontinuation and restarting needs to be documented. If temporary discontinuation is due to an AE, it should be reported to the Sponsor-designated medical monitor.

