#### 10.3.2.4. Treatment Compliance

The proportion of patients who are significantly noncompliant as noted in Section 7.6 of this protocol will be summarized and compared among all treatment groups using Fisher's exact test.

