6.16. Protocol Violations

Listings of subjects with significant protocol violations will be provided for the Randomized Population.

The following list of significant protocol violations will be programmed against the clinical database:

- Informed consent violation detected as a missing date of informed consent
- Did not have an assessment of the primary endpoint at any of the visits at which the scale was scheduled to be assessed
- Not compliant with study drug calculated as taking less than 80% or greater than 120% of study drug while the subject was expected to be on treatment

The following list of significant protocol violations will be determined by clinical/medical group:

Protocol violations of inclusion/exclusion criteria

- Study dosing algorithm violation (such as if subjects randomized to treatment A were given treatment B or subjects randomized to treatment A never received the assigned study drug.)
- Unqualified raters for the primary endpoint

Other protocol violations reported through the monitoring process will be reviewed by the study team and if judged to be significant, will be added to the final reported listing.

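### SAP 6.9 counts intake above 120% as compliant while SAP 6.16 lists it as non-compliant, so the planned between-arm compliance test cannot show a difference in over-taking (minor)

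*SAP*

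**What the plan says.** Four places bear on this point.

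- **SAP 6.9** defines compliance with a lower bound only: "Subjects who consume at least 80% of the prescribed daily dose during this study will be considered compliant". The population is fixed ("Treatment compliance will be assessed in the Safety – PC population"), and so is the test: "The percentage of compliant subjects will be compared across treatment groups using Fisher's Exact test".
- **SAP 6.16**, in the list of violations to be programmed against the database, uses two bounds: "Not compliant with study drug calculated as taking less than 80% or greater than 120% of study drug". It counts only time when the patient should have been on treatment, and the listing covers the Randomized population.
- **Protocol 7.6** has the same 80% floor for being compliant. It then adds, opening with the word Similarly, that a patient is significantly noncompliant if "judged by the investigator to have intentionally or repeatedly taken more than the prescribed amount of medication". That category has no percentage attached.
- **Protocol 10.3.2.4** names the quantity to be compared among arms by Fisher's exact test: "The proportion of patients who are significantly noncompliant as noted in Section 7.6".

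**The concern.** One report would give two answers for the same patient. Someone who took 130% of study drug counts as compliant in the 6.9 table and appears as a significant violator in the 6.16 listing.

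The test is affected as well as the label. Because 6.9 places over-takers with patients who took exactly what was prescribed, its Fisher comparison reacts only to under-taking. Over-taking is the behaviour that protocol 7.6 expressly calls significant noncompliance, and protocol 10.3.2.4 promises a comparison of that group. As the SAP stands, no between-arm comparison of over-taking is specified. At stake is whether the compliance table describes drug intake in each arm in a way that agrees with the rest of the report.

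**Working it through.** No compliance rate, or sample size based on compliance, is stated in either document, so there is no plan figure to reproduce. The check is to apply the rules side by side and then see what the choice could change.

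**Step 1. Classification by percentage intake x.** SAP 6.9: compliant if x ≥ 80. SAP 6.16: non-compliant if x < 80 or x > 120.

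| Intake x | SAP 6.9 | SAP 6.16 |
|---|---|---|
| 70%, 79.9% | not compliant | not compliant |
| 80%, 100%, 110%, 120% | compliant | compliant |
| 120.1%, 130% | compliant | not compliant |

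The rules disagree exactly for x > 120. Intake from 100% to 120% is compliant under both.

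**Step 2. Which tail each comparison can see.** The 6.9 test separates x < 80 from everything else. Protocol 10.3.2.4, read literally with 7.6, separates investigator-judged over-taking from everything else. The 6.16 rule captures both tails, but it feeds a listing and has no test attached.

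**Step 3. Illustration.** Inputs: n = 633 per arm, the planned number in protocol 10.1 and SAP 5.2. Assumed: 5% under-takers in each of two arms (0.05 × 633 ≈ 32), and over-takers above 120% at 1% in one arm (≈ 6) against 2% (≈ 13) or 4% (≈ 25) in the other. The x > 120 group stands in for the protocol's judged category.

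Percentage compliant:
- Under 6.9: (633 − 32)/633 = 94.9% in both arms, whatever the number of over-takers.
- Under 6.16, with 6 over-takers: (633 − 38)/633 = 94.0%.
- Under 6.16, with 13: (633 − 45)/633 = 92.9%.
- Under 6.16, with 25: (633 − 57)/633 = 91.0%.

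Two-sided Fisher p:

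| Over-takers | 6.9 rule | 6.16 rule | Over-takers only |
|---|---|---|---|
| 6 vs 13 | 1.00 | 0.50 | 0.16 |
| 6 vs 25 | 1.00 | 0.054 | 0.0008 |

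The 6.9 result does not move, by construction. The last column shows why the two tails are better reported separately: even the two-sided rule dilutes an imbalance confined to one tail.

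**The case against.** The strongest reply is that nothing inferential depends on this. The primary model in SAP 6.12.1.1 has no compliance term, SAP 6.6 keeps no per-protocol population, SAP 6.15 has no compliance subgroup, and SAP 6.1 says no test will be interpreted as statistically significant. The 6.9 floor also matches the protocol's own definition of a compliant patient. All of that stands and keeps the point minor. It does not remove the contradiction between two current sections of one SAP.

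Several stronger readings are tempting, and the documents do not support them.

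- *That 6.9 is the only check on drug delivery.* It is not. The SAP summarises days of exposure by arm (6.13.1) and models plasma Aβ by arm (6.14.1), and protocol 9.5 provides plasma drug and metabolite concentrations.
- *That over-use is hidden.* Patients above 120% are listed under 6.16. What is missing is a summary row and a comparison.
- *That protocol and SAP test strictly opposite tails.* That is the literal reading. The word Similarly in 7.6 may have been meant to make over-taking a second route to noncompliance alongside intake below 80%, in which case 10.3.2.4 would cover both tails.
- *That a pooled tablet count could pass a patient who took only 60% of the active tablets.* The protocol does say "the investigational product will be blinded using double-dummy technique", and (100% + 60%)/2 = 80%. But neither document says that counts are pooled across tablet types, or that they are recorded by type.
- *That a permitted interruption alone makes a patient non-compliant under 6.9.* Protocol 8.1.2 says "The maximum permissible treatment suspension is a total of 6 weeks over the duration of the study", and 42/0.20 = 210 days. This requires suspended days to count as prescribed. No text says so, and the more natural reading is that they do not.

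The SAP revision history also records that compliance summaries and analyses were deleted. A change log describes superseded text, so the mismatch is not counted as an error here. It does leave open whether 6.9 is meant to be run.

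**Conclusion.** The point holds in a narrow form. SAP 6.9 and 6.16 classify intake above 120% in opposite ways, and only such intake. The 6.9 comparison cannot show a between-arm difference in over-taking, the group that protocol 7.6 and 10.3.2.4 single out. This follows from the text and needs no assumption.

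Its numerical size is unknown, because the documents give no frequency of intake above 120%. The Fisher figures rest on assumed counts at the planned arm size. They show that the reported result can depend on the rule; they do not predict that it will. The protocol's over-taking category is also a matter of investigator judgement, whereas 6.16 uses a calculated cut, so the two need not identify the same patients.

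Severity is minor: one descriptive table is affected, and the efficacy conclusions are not.

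**What to change.** First confirm whether SAP 6.9 will be run. If not, remove it. If so:

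1. Use the 6.16 definition in 6.9: compliant means 80% to 120% of study drug, counted over the time the patient was expected to be taking it and limited to the placebo-controlled period.
2. Report below 80% and above 120% as separate rows by arm.
3. Add a sentence on how this relates to protocol 7.6 and 10.3.2.4. It should say whether the above-120% row stands in for the investigator-judged category, and whether intake below 80% was meant to be part of the protocol comparison.

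No protocol amendment appears necessary. Protocol 10.3.1 lets analysis changes that do not alter a principal feature be described and justified in the SAP and the study report.

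The cost is a few lines of SAP text and some programming, since 6.16 already requires each patient's intake to be calculated against both bounds. The downside is that the stated compliance percentage may come out slightly lower.

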6.10. Concomitant Therapy

Concomitant medications will be summarized for the Safety – PC population. A summary of concomitant medications will be presented as frequencies and percentages for each treatment group. Fisher's Exact test will be used to test for treatment differences between groups. If the start or stop dates of therapies are missing or partial to the degree that determination cannot be made of whether the therapy is prior or concomitant, the therapy will be deemed concomitant. Concomitant medications will be listed by subject with both the Placebo-Controlled and Delayed-Start periods combined.

A summary table will also be provided for AChEI/memantine medications. Medications will be coded using the current version of the World Health Organization (WHO) drug dictionary.

6.11. Study Partners

Study partners will be summarized for the Safety – PC population. The protocol states every effort should be made to keep the same study partner throught the duration of this trial. However, changes may be unavoidable. The percentage of subjects with the same study partner will be compared across treatment groups using a Fisher's Exact test. Additionally, study partner changes will be categorized (0 changes, 1 change, and more than 1 change) and compared using Pearson's chi-square test.

6.12. Efficacy Analyses

6.12.1. Placebo-Controlled Treatment Period

6.12.1.1. Primary Efficacy Analysis

The primary objective of this study and of the Placebo-Controlled period is to test the hypothesis that at least one dose of LY3314814 will slow the clinical decline of AD as compared to placebo in patients with mild AD dementia. This objective will be assessed on the Evaluable – PC population using an MMRM analysis of the ADAS-Cog13 in patients with mild AD at baseline, in which the specific hypothesis is that the decline from baseline at the end of the placebo-controlled treatment period (78 weeks) for at least one dose of LY3314814 will be significantly less than that for placebo.

The change from baseline score on the ADAS-Cog13 at each scheduled postbaseline visit (according to the Study Schedule) during the Placebo-Controlled period will be the dependent variable. The model for the fixed effects will include terms for: baseline score, pooled site, treatment, visit, treatment-by-visit interaction, baseline-by-visit interaction, concomitant AChEI and/or memantine use at baseline (yes/no), and age at baseline. Visit will be considered a categorical variable with values equal to the visit numbers at which the ADAS Cog13 was assessed.

The null hypothesis is that the contrast between both LY3314814 dose groups versus placebo at the last visit equals zero. An unstructured covariance matrix will be used to model the within-subject variance-covariance structure. If the unstructured covariance matrix results in a lack of convergence, the following tests will be used in sequence: heterogeneous Toeplitz covariance structure, heterogeneous autoregressive covariance structure, heterogeneous compound symmetry covariance structure.

The Kenward-Roger approximation will be used to estimate the denominator degrees of freedom.

6.12.1.2. Secondary Efficacy Analyses

The additional clinical and outcome measurements listed below will be analyzed separately using an MMRM analysis. The change from baseline at each scheduled postbaseline visit will be the

dependent variable. The model for the fixed effects will include terms for the 8 independent effects listed previously (Section 6.12.1.1) The null hypothesis is that the differences in least-squares means between the LY3314814 dose groups versus placebo at Week 78 equal zero. The outcomes that will be analyzed are:

- Change from baseline as obtained from the ADAS-Cog₁₁.
- Change from baseline in ADCS-ADL total score, the instrumental ADL subscale, and the basic ADL subscale.
- Change from baseline in CDR Sum of Boxes
- Change from baseline in MMSE
- Change from baseline in FAO
- Change from baseline in behavioral disturbance as measured by NPI (12 item) total score (frequency multiplied by severity).
- Change from baseline in RBANS Total, Immediate Memory, Delayed Memory, Visuospatial/Construction, Language, and Attention scores.

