- 12. Deleted table of analyses AZET.SAP.2 and renumbered tables.
- 13. Delayed-start summary and analysis descriptions have been deleted throughout the SAP where appropriate.
- 14. Kaplan-Meier summaries of disposition have been deleted (see section 6.7).
- 15. ADAS-Cog11 was added to the baseline summaries.
- 16. Planned output for prior medications and anticholinergic medications have been removed (see section 6.10).
- 17. Deleted the graphical method for hypothesis testing of key secondary objectives and revised the description of secondary analyses.
- 18. Deleted all slope analyses.
- 19. Deleted all time-to-progression analyses.
- 20. Deleted all exploratory analyses.
- 21. Deleted all sensitivity analyses.
- 22. Deleted compliance summaries and analyses.
- 23. Added a note about p-values in the delayed-start safety summaries.
- 24. Applied some editing in section 16.3.2 to clarify the handling of TEAEs.
- 25. Changed the reporting of common AEs from 5% to 2%.

- 26. In AEs of special interest, revised the skin disorders cluster.
- 27. Subgroup analyses of TEAEs are deleted.
- 28. Added a summary of PCS laboratory results.
- 29. The threshold for weight gain or loss was change from 4% to 7%.
- 30. Added a shift table for white matter changes detected through MRIs.
- 31. The description of the CSSRS analysis has been completely revised (see section 6.13.8).
- 32. Added summaries to the skin evaluation analyses.
- 33. Added detail to the eye examination analysis description.
- 34. Deleted subgroup analyses of plasma Aβ.
- 35. Deleted correlation calculations between imaging results and ADAS-Cog₁₁ and ADAS-Cog₁₂.
- 36. Revised the description of amyloid PET analysis.
- 37. Revised the description of the FDG PET analysis and added the perfusion analysis.
- 38. Revised the description of TAU PET analysis.
- 39. Revised the description of vMRI analysis
- 40. Deleted a selection of subgroup analyses.
- 41. Deleted appendix of drugs with anticholinergic properties.
- 42. There will no longer be any per-protocol population analyses so the wording of section 6.16 has been amended to reflect the protocol violations that will be listed for the final report.
- 43. Added two references.
- 44. Minor editing for grammar and clarity throughout.

4. Study Objectives

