4.2. Secondary Objectives – Placebo-Controlled Period

4.2.1. Secondary Clinical Efficacy Objectives

The secondary clinical efficacy objectives of the Placebo-Controlled period of AZET include:

- Evaluation of the efficacy of LY3314814 in patients with mild AD dementia on functional, clinical, and cognitive outcomes (ADCS-iADL, FAQ, iADRS, CDR-SB, CDR-Global, NPI, and MMSE) at the end of the Placebo-Controlled period (Week 78).
- Evaluation of the relationship between the treatment effect of LY3314814 and time on functional, clinical, and cognitive outcomes (ADAS-Cog13, ADCS-iADL, FAQ, CDR-SB, and iADRS) at points other than the end of the Placebo-Controlled period.

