6.3. Handling of Dropouts or Missing Data

6.3.1. Handling Missing Data from Subject Dropouts

A likelihood-based mixed effects model for repeated measures will be used to handle missing data. The model parameters are simultaneously estimated using restricted likelihood estimation incorporating all of the observed data. Estimates have been shown to be unbiased when the missing data are missing at random and when there is ignorable non-random missing data.

Repeated measures analyses will only use data from visits where the data was scheduled to be collected (see Andersen and Millen 2013). When subjects discontinue from the study early, there may be efficacy or safety data measurements at visits where the variables were not scheduled to be collected. These data will be used in all other analyses.

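### SAP 6.12.1.2 sets a Week 78 contrast for RBANS, which is last scheduled at Week 71, and leaves out iADRS although SAP 4.2.1 still lists it as a secondary outcome

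*SAP*

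**What the plan says.** **RBANS.** SAP 6.12.1.2 fits a separate MMRM to each listed outcome, with change from baseline at scheduled visits as the response and the fixed effects of the primary model. One null hypothesis serves them all: that the adjusted mean differences for the "dose groups versus placebo at Week 78 equal zero". The last item on the list is "Change from baseline in RBANS Total, Immediate Memory, Delayed Memory, Visuospatial/Construction, Language, and Attention scores". SAP 6.3.1 restricts what the models may use: "Repeated measures analyses will only use data from visits where the data was scheduled to be collected". Protocol Table 2.2 marks RBANS at Visit 2, Visit 11 (Week 45), Visit 15 (Week 71) and early discontinuation, and leaves Visit 16 (Week 78) blank.

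**iADRS.** The first objective in SAP 4.2.1 covers "ADCS-iADL, FAQ, iADRS, CDR-SB, CDR-Global, NPI, and MMSE) at the end of the Placebo-Controlled period (Week 78". The second covers "ADAS-Cog13, ADCS-iADL, FAQ, CDR-SB, and iADRS) at points other than the end of the Placebo-Controlled period". Protocol 10.3.3.3.2 names iADRS among the outcomes to be analysed with the primary MMRM and counts that analysis as key secondary. The only mention of iADRS in SAP section 6 is the baseline severity summary in 6.8: "iADRS, CDR Sum of Boxes, RBANS, NPI, RUD-Lite, EQ-5D Proxy, and FAQ". The nearest entry in the SAP revision history is item 17: "Deleted the graphical method for hypothesis testing of key secondary objectives and revised the description of secondary analyses". It does not name iADRS.

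**CDR-Global.** It remains in the first 4.2.1 objective. Protocol 10.3.3.4 gives it a time-to-progression analysis, and revision item 19 deletes all analyses of that type.

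**The concern.** The RBANS instruction asks for an estimate at a visit where the scale is not given. A programmer following it literally gets a non-estimable contrast and must then choose a substitute without guidance from the plan. RBANS is not forgotten text: revision item 8 added missing-item rules for it in this version, so the sponsor intends to report it.

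The iADRS gap means that a team following section 6 would leave a current objective unanswered. Protocol 10.3.1 says that changes to analysis methods not needing an amendment are to be described and justified in the SAP and the study report, and no iADRS justification appears. If an iADRS result were produced later, it would look unplanned, although the protocol planned it.

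**Working it through.** There is no stated figure to reproduce, so the check sets the schedule against the analysis text.

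**1. Assessments in the Placebo-Controlled period (protocol Table 2.2, read by column)**

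| Scale | Scheduled weeks after baseline | Week 78? |
|---|---|---|
| ADAS-Cog | 13, 26, 39, 52, 65, 78 | yes |
| ADCS-ADL | 26, 52, 78 | yes |
| CDR | 26, 52, 78 | yes |
| MMSE | 13, 26, 52, 78 | yes |
| FAQ | 26, 52, 78 | yes |
| NPI | 26, 52, 78 | yes |
| RBANS | 45, 71 | no |

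The last RBANS visit precedes the stated contrast by 78 − 71 = 7 weeks.

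**2. Estimability.** With visit as a category, the contrast of dose k against placebo (0) at visit v is

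(τ_k − τ_0) + (τν_kv − τν_0v),

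where τ is the treatment effect and τν the treatment-by-visit term. For RBANS, v takes only the values Visit 11 and Visit 15. There is no τν term for Visit 16, so the contrast is undefined. A model with continuous time could extrapolate, but revision item 18 deleted the slope analyses.

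**3. Could early-discontinuation records supply Week 78?** SAP 6.3.1 rules them out of repeated measures models. They would also be sparse near Week 78: footnote c of Table 2.2 calls for RBANS at that visit only if more than 12 weeks have passed since the last one, and a patient tested at Week 71 would be 7 weeks on.

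**4. Extent.** The 6.12.1.2 list has 7 bullets, of which 1 (RBANS) has no Week 78 visit. By score, the list holds ADAS-Cog11 1, ADCS-ADL 3, CDR-SB 1, MMSE 1, FAQ 1, NPI 1 and RBANS 6, so 1 + 3 + 1 + 1 + 1 + 1 + 6 = 14. Six of the 14 scores are affected. With two doses, that is 12 of 28 Week 78 comparisons.

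**5. iADRS.** The SAP contains these uses:

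- Objectives (4.2.1): both of the two clinical efficacy objectives.
- Baseline summary (6.8): yes.
- Post-baseline analysis in section 6: none. Section 6.12.2.1 also excludes any Delayed-Start efficacy summary, so that period does not fill the gap.

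Revision item 2 removed two secondary objectives from this period. Protocol Table 4.1 has four clinical efficacy objectives and SAP 4.2.1 has two; the absent ones are the slope objective and time in the current disease state. The objectives naming iADRS were kept.

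The iADRS needs ADAS-Cog13 and ADCS-iADL at the same visit. The weeks common to {13, 26, 39, 52, 65, 78} and {26, 52, 78} are 26, 52 and 78. Both components are also taken at Visit 2, so a baseline exists.

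**The case against.** The best reply is that both points are drafting matters in a stopped study. SAP 6.1 says no test will be read as significant, and 6.1.1 calls all results hypothesis-generating. Protocol 9.1.3 places RBANS among the other and exploratory assessments, and it is not in the 4.2.1 objectives. Its model still gives valid Week 45 and Week 71 estimates, and Week 71 is the obvious substitute. Both iADRS components keep their own MMRM. All of this stands, and it limits the weight of the point. It does not make the RBANS contrast estimable, nor does it explain why iADRS is left out while ADAS-Cog11, basic ADL and RBANS are modelled.

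Three stronger readings are tempting and fail:

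- *CDR-Global was dropped without a reason.* The only analysis the protocol specifies for it is time to progression (10.3.3.4); 10.3.3.3.2 does not include it among the MMRM outcomes. Revision item 19 deletes time-to-progression analyses, which largely explains its absence. CDR-SB, built from the same six boxes, is still modelled.
- *The primary analysis was worded to avoid the problem.* SAP 6.12.1.1 does put its contrast "versus placebo at the last visit equals zero", but the same section fixes that point at 78 weeks, and ADAS-Cog13 is assessed at Visit 16. There was nothing to avoid.
- *iADRS has no planned analysis anywhere.* The protocol has one. The gap is that the SAP neither repeats it nor says it was withdrawn.

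**Conclusion.** The point holds in two parts. First, the Week 78 RBANS contrast in SAP 6.12.1.2 cannot be estimated under the visit schedule and the SAP's own rule on off-schedule data; this touches 1 of 7 listed outcome bullets. Second, iADRS is a current secondary outcome in both 4.2.1 objectives and has a planned MMRM in the protocol, but no post-baseline analysis in the SAP and no stated reason for the omission. CDR-Global is a minor leftover in the objectives list.

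The impact is low: the primary and safety analyses are unaffected and type I error is not at issue. A reader might infer that iADRS was removed selectively. The documents do not support that, because item 17 is too general to show either a deliberate drop or an oversight. The conclusion rests on the current texts of SAP 4.2.1 and section 6 and on Table 2.2 as read by column.

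**What to change.** 1. In SAP 6.12.1.2, state that for RBANS the treatment contrast is at Visit 15 (Week 71), its last scheduled assessment in the Placebo-Controlled period. Cost: one sentence.
2. Add change from baseline in iADRS to the 6.12.1.2 MMRM list, at Weeks 26, 52 and 78, scored as described in protocol 9.1.2 (unweighted, 0 to 141, higher meaning greater impairment; component maxima 85 + 56 = 141). Cost: one extra model on data already collected.
3. Align the CDR-Global entry in SAP 4.2.1 with the deletion recorded under revision item 19. Cost: wording only.

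All three belong in the SAP before final unblinding, the point by which the revision history says Version 3 is to be approved.
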